9.3 Sample Size Considerations for the Year 2 Extension Study

For safety assessment, Table 6 shows the precision for estimating the AE rate within each arm of 42 participants for a range of underlying event rates.

Table 6. Exact 95% CI of AE rate estimate within each arm of size 42.

Observed		95% confidence interval	
number of	Observed	Lower	Upper
events	event rate	bound	bound
0	0	0	0.084

Version Date: 14 March 2024

1	0.024	0.001	0.126
2	0.048	0.006	0.162
3	0.071	0.015	0.195
4	0.095	0.027	0.226
5	0.119	0.04	0.256
6	0.143	0.054	0.285
7	0.167	0.07	0.314
8	0.19	0.086	0.341
9	0.214	0.103	0.368
10	0.238	0.121	0.395
11	0.262	0.139	0.42
12	0.286	0.157	0.446
13	0.31	0.176	0.471
14	0.333	0.196	0.495

With 42 participants per arm, there is 90% power to detect the difference between two arms if the event rate is 0.01, 0.05, or 0.1 in one arm and no less than 0.24, 0.33, or 0.42 in the other arm, respectively, based on two-sided proportion test at significance level 0.05.

Table 7 shows the power for comparing two arms on the primary efficacy endpoint, namely, the time from receiving the second dose of L9LS (or placebo) to the first Pf blood-stage infection during extension study with each arm of 42 participants.

Table 7. Power for between-arm comparison on time to infection based on two-sided log rank test at significance level 0.05.

Infection rate	Infection rate in		
in one arm	the other arm	Relative efficacy	Power (%)
0.5	0.2	0.6	79
0.5	0.15	0.7	90
0.6	0.24	0.6	89
0.6	0.18	0.7	96
0.7	0.28	0.6	96
0.7	0.21	0.7	99

9.4 Populations for Analyses

The following datasets will be considered in study analyses:

• Intention-to-treat (ITT) analysis dataset will include all subjects that receive assignment and will be analyzed according to the initial randomization assignment.

Version Date: 14 March 2024

Modified intention-to-treat (MITT) analysis dataset will include all randomized subjects
that receive the study intervention and will be analyzed according to the initial
randomization assignment.

 Per-protocol (PP) analysis dataset will include all randomized subjects that receive the study intervention consistent with the initial randomization assignment and complete the scheduled visits, and will be analyzed according to the initial randomization assignment.
 In cases where subjects receive an intervention other than the one randomly assigned, an as-treated analysis will be additionally performed according to the actual product received.

9.4.1 Evaluable for toxicity

All participants will be evaluable for toxicity from the time of their first treatment with L9LS or placebo. The toxicity analysis will be ITT.

9.4.2 Evaluable for objective response

Not applicable.

9.4.3 Evaluable Non-Target Disease Response

Not applicable.

9.5 Statistical Analyses

9.5.1 General Approach

In general, descriptive statistics will be tabulated by treatment arm for endpoints of interest. This will include point estimates (mean, geometric mean, median, or proportions) and their respective 95% CIs. Formal comparisons will use standard methods, contingency tables for categorical variables, t-tests for comparing means if data follow a normal distribution or geometric means if data after log transformation follow a normal distribution, or nonparametric analogs for comparing medians. Unless specified in the subsequent sections, comparisons will be two-sided with type I error rate of 0.05.

Missing data will be considered as "missing completely at random" provided the amount of missing data is modest (e.g., <10%). We will examine the "missing completely at random" assumption if the amount of missing data is more than 10%. If the assumption does not hold, missing data will be handled under the "missing at random" assumption (that is, missingness depends only on observed variables) via methods such as multiple imputation and inverse propensity weighting. To handle the possibility of "missing not at random," a sensitivity analysis will be performed by imputing missing binary observations with the observed proportion in the opposite arm. A secondary sensitivity analysis will be considered by imputing missing binary observations as failures.

Version Date: 14 March 2024

Randomization: Weight-stratified randomization will be implemented in the dose-escalation study and the efficacy study. In the efficacy study, 75 participants will be recruited into each weight group (15-19 kg, 20-25 kg, and 26-30 kg). Within each weight group, randomization will be 1:1:1 allocation to the 2 L9LS arms and the placebo arm. The total number of participants will be 75 in each arm (25 of weight 15-19 kg, 25 of weight 20-25 kg, and 25 of weight 26-30 kg). A similar stratified randomization will be applied to the dose-escalation study: six participants in each weight group, starting with 26-30 kg, followed by 20-25 kg, and then 15-19 kg, will be recruited and randomized 1:1 to receive L9LS at the dose of 150 mg or placebo; if no safety concerns arise, randomization into the L9LS at the dose of 300 mg or placebo ensues in the same manner. To limit the number of dropouts before L9LS administration, randomization and L9LS administration will occur as close in time as possible.

9.5.1.1 Year 2 Extension Study

The same analysis methods for safety, PK, and efficacy endpoints described for the original study (year 1) below will be applied to the year 2 extension study. There will be no multiplicity adjustment in extension study analyses. All comparisons will be conducted at two-sided significance level 0.05.

9.5.2 Analysis of the Primary Endpoints

Analysis for the primary endpoint for safety and tolerability is described in section 9.5.5.

Analysis for the primary efficacy endpoint, protective efficacy with Pf infection determined by blood smear, is described in section 9.5.4.

9.5.3 Analysis of the Secondary Endpoint(s)

Analysis of the secondary efficacy endpoints, incidence of Pf infection determined by RT-PCR, is described in section 9.5.4.

Analyses of the secondary endpoints for the PK of L9LS and the association of L9LS concentration with Pf infection risk are described in section 9.5.6.

9.5.4 Efficacy Analyses

The primary efficacy endpoint (efficacy study primary endpoint) is the incidence of malaria infection defined as blood smear—positive Pf infection between 1 week and 24 weeks after administration. The secondary efficacy endpoints are the incidence of malaria infection as determined by RT-PCR and the incidence of clinical malaria. The efficacy analyses will be MITT over participants in the efficacy study.

Version Date: 14 March 2024

The primary efficacy analysis will be based on time to the first infection. The survival patterns will be described by Kaplan-Meier curves for each arm and compared by the logrank test across different arms. The protective efficacy of the study product will be estimated by the hazard ratio from the Cox proportional hazards model. These analyses will be carried out by R packages that account for interval censoring: package "interval" for deriving a nonparametric maximum likelihood estimation based on the Kaplan-Meier survival curve and logrank test, and package "icenReg" for Cox proportional hazards regression. To address the heterogeneity of the study population, a Cox regression with regressors other than the study arm will be additionally performed to account for potential differences among participants. The regressors will include time of enrollment and possibly those covariates that are significantly different between the study product arms and the placebo arm in spite of randomization. An additional Cox regression will be performed with pre-existing parasitemia (Pf infection status determined by blood smear at baseline) as the stratification variable. The Holm method will be adopted to handle the issue of multiplicity in comparing the two dose arms against the placebo.

The secondary efficacy analysis will be based on the proportion of infection. The proportion of infection will be estimated for each arm and compared across arms based on Kaplan-Meier estimates assuming events occur at the time they are detected: the proportion of infection by one minus the Kaplan-Meier estimate in the arm, and the vaccine efficacy by one minus the relative risk of infection with melding method for constructing the melded 95% CI of the vaccine efficacy.³⁷

Since this trial adopts weight-stratified randomization, participants cover the dose range from 5 mg/kg to 20 mg/kg. In addition to the above efficacy analyses that compare each dose arm with the placebo arm, an exploratory analysis will be additionally conducted to assess how dosage, in terms of mg of L9LS per kg of subject body weight, affects the protective efficacy.

The above analyses will apply to both the primary and the secondary efficacy endpoints.

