The second part of the study is a weight-stratified, randomized, double-blind, placebo-controlled trial to assess safety and protective efficacy of L9LS and placebo in children 6-10 years of age. In this part of the study, 225 subjects will be randomized 1:1:1 to SC administration of 150 mg of L9LS (n=75), 300 mg of L9LS (n=75), or placebo (n=75). Randomization of subjects in each arm will be weight-stratified (26-30 kg, n=75; 20-25 kg, n=75; 15-19 kg, n=75). Subjects in the efficacy study will receive the study agent and be followed at study visits over 24 weeks. Primary study assessments include medical history, physical examination, and blood collection for identification of Pf infection and other research laboratory evaluations.

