4.3 Justification for Dose

The doses used in this study were selected based on preclinical data and data generated in the ongoing phase 1 VRC study, which tested the dose range included in this protocol. This study will test fixed doses of L9LS in children in a defined range of subject weights to approximate the weight-based dosing used in the phase 1 VRC study. Compared to weight-based dosing, fixed dosing will provide a greater range of antibody concentrations in vivo for determining a protective L9LS titer. Fixed dosing is also simpler to administer, reduces the risk of medication errors, and is generally more cost effective—factors that are relevant to the potential use of L9LS in malaria-endemic regions.

Version Date: 14 March 2024

In the safety study, subjects aged ≥18 years weighing 60 kg or less will receive a SC dose of 300 mg (2 mL) or 600 mg (4 mL), approximating the weight-based dosing of 5 mg/kg and 10 mg/kg, respectively, in a 60-kg adult. An additional group of subjects aged ≥18 years weighing 60 kg or less in the safety study will receive an IV dose of 20 mg/kg. This dose will be administered IV rather than SC because 4 mL is the maximum volume of L9LS that will be administered SC in this study. In Kalifabougou, the average weight of adult females and males is 55.6 kg and 61.7 kg, respectively. In the safety and efficacy studies, subjects aged 6-10 years weighing ≥15 kg and ≤30 kg will receive a dose of 150 mg or 300 mg SC, approximating the weight-based dosing of 5 mg/kg and 10 mg/kg, respectively, in a 30-kg child, and 10 mg/kg and 20 mg/kg, respectively, in a 15-kg child. Based on recent data from the study site, approximately 85% of children aged 6-10 years in Kalifabougou weigh between 15 kg and 30 kg. The doses used in the efficacy study will complement the data generated in the ongoing phase 1 VRC study. The doses used in the phase 1 VRC study were derived from 1) efficacy data from the challenge studies performed in mice showing that the protective concentration of antibody in vivo is between 5-100 µg/mL in 2 different mouse models of malaria infection; 11 and 2) PK data from nonhuman primate studies with L9LS and prior clinical experience in healthy adults with human MAbs targeting HIV (i.e., VRC01, VRC01LS, and VRC07-523LS) and ebolavirus (MAb114) at the same dose.

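### Year 1 efficacy randomisation is stratified by weight group, but no log-rank or Cox analysis in 9.5.4 uses it, and the additional Cox model picks covariates by imbalance from no stated list

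*Combined protocol and SAP*

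**What the plan says.** Section 9.5.1 describes the efficacy-study allocation: "Within each weight group, randomization will be 1:1:1 allocation to the 2 L9LS arms and the placebo arm". The planned numbers are 25 children per arm in each of the 15-19, 20-25 and 26-30 kg groups. Section 4.1 describes the same stratification.

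Section 9.5.4 gives the primary comparison: "The survival patterns will be described by Kaplan-Meier curves for each arm and compared by the logrank test across different arms". Protective efficacy comes from a Cox hazard ratio, and both are run with methods for interval-censored data. No stratum or covariate is named for either.

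Two further Cox models follow. In the first, "a Cox regression with regressors other than the study arm will be additionally performed to account for potential differences among participants". Its content is set by this sentence: "The regressors will include time of enrollment and possibly those covariates that are significantly different between the study product arms and the placebo arm". The second is stratified by baseline parasitemia.

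Weight appears in the efficacy analyses only in an exploratory analysis to "assess how dosage, in terms of mg of L9LS per kg of subject body weight, affects the protective efficacy".

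For tests in general, section 9.5.1 sets a default: "Unless specified in the subsequent sections, comparisons will be two-sided with type I error rate of 0.05". Section 9.5.7 makes baseline comparisons descriptive and lists no covariates.

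**The concern.** There are two gaps.

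1. **The randomisation strata are not used in the analysis.** When a stratification factor predicts outcome, an unstratified test overstates the variance of the treatment comparison. It then becomes conservative and loses some power. The additional Cox model does not close the gap. It admits covariates that are significantly imbalanced, and stratified allocation makes weight the covariate least likely to qualify.

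2. **The covariate rule is open.** Only time of enrollment is certain to enter. The default level in 9.5.1 supplies a threshold. The plan does not say which covariates are candidates, whether the two L9LS arms are pooled or each is tested against placebo, or what *possibly* means. The content of this supportive model is therefore settled after baseline data are compared by arm. Significant imbalance in a randomised trial is also no guide to whether a covariate predicts infection.

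**Working it through.** **Inputs from the documents.** 75 per arm, 25 per weight group per arm (9.5.1). Two-sided 0.025 per dose, 10% dropout, placebo rate 0.4, protective efficacy (PE) 0.7 defined as one minus the relative risk (9.2.2). Scheduled visits at days 7, 14, 21 and 28, then every 14 days to 168 (1.3.3).

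**Step 1: reproduce the plan's power.** With p1 = p0(1 − PE), HR = ln(1 − p1)/ln(1 − p0), D = 0.9 × 75 × (p0 + p1), and Freedman's formula Φ(√D(1 − HR)/(1 + HR) − 2.241):
- PE 0.7: p1 = 0.12, HR = 0.250, D = 35.1, power 90.5%. The plan states 91% in Table 4 and 90% in the text.
- PE 0.6: p1 = 0.16, HR = 0.341, D = 37.8, power 78.2%. Table 4 states 78%.

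The formula is within 2 points in all 18 rows of Table 4. The simulated power in Step 2 is higher because Freedman's formula is conservative at hazard ratios this small. The quantity of interest is the difference between the two tests.

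**Step 2: unstratified against weight-stratified test.** The documents give no relation between weight and infection, so the hazard step between adjacent weight groups is assumed: none, 1.5-fold or 2-fold, with lighter children at higher risk. A 2-fold step is a 4-fold gradient from lightest to heaviest. The simulation used exponential infection times calibrated to the average placebo rate, exponential dropout, and visits missed with probability 0.1 (assumed). The test was an interval-censored log-rank score with permutation variance; the stratified version sums scores and variances within groups. There were 10,000 trials per power scenario and 20,000 per null scenario. Each entry is unstratified vs stratified, in percent.

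| Scenario | No step | 1.5-fold | 2-fold |
|---|---|---|---|
| Power, placebo 0.4, PE 0.7 | 95.2 vs 95.1 | 95.1 vs 95.4 | 95.1 vs 96.0 |
| Power, placebo 0.4, PE 0.6 | 84.5 vs 84.4 | 83.5 vs 84.3 | 82.3 vs 85.2 |
| Power, placebo 0.7, HR 0.5 | 81.2 vs 80.9 | 78.1 vs 80.3 | 73.7 vs 81.7 |
| Null, placebo 0.4 (nominal 2.5) | 2.5 vs 2.5 | 2.3 vs 2.6 | 1.6 vs 2.3 |
| Null, placebo 0.7 (nominal 2.5) | 2.5 vs 2.6 | 2.0 vs 2.3 | 1.3 vs 2.5 |

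The third row is off-design: PE there is 1 − (1 − √0.3)/0.7 = 0.354, weaker than any row of Table 4.

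**Step 3: where stratifying loses.** These scenarios let efficacy vary by weight.
- Hazard ratios 0.35/0.5/0.7 from light to heavy, placebo 0.7, no placebo gradient: 79.4 vs 77.8%, a loss of 1.6 points.
- Hazard ratios 0.2/0.34/0.55, placebo 0.4, no placebo gradient: 81.7 vs 81.1%.
- Hazard ratios 0.35/0.5/0.7, placebo 0.7, 1.5-fold step with heavier children riskier: 72.0 vs 70.6% (6,000 trials). An ordinary stratified log-rank on the same data gives 71.9%, so this loss depends on the version of the test.
- The first set of hazard ratios with lighter children riskier by a 1.5-fold step: 81.3 vs 84.3%, a gain.

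**Step 4: the hazard ratio.** At placebo 0.4, PE 0.7 and a 2-fold step, the median estimate is 0.264 without weight group and 0.246 with it; the weight-conditional value is 0.250. The large-sample limit of the unadjusted Cox model solves ∫G[f1 − (f0 + f1)·S1e^β/(S1e^β + S0)]dt = 0. Here S and f are each arm's survival and density averaged over the three weight groups, and G is retention, falling to 0.9 at day 168. The solution is HR = 0.264, equal to the unadjusted median. At PE 0.6 the limit is 0.358 against a simulated 0.353. The standard error of the log hazard ratio at the design point is 0.383 without and 0.384 with weight group.

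**Step 5: chance selection of covariates.** Assume 5 or 10 independent candidates tested at 0.05.
- L9LS arms pooled: 1 − 0.95^5 = 0.226; 1 − 0.95^10 = 0.401.
- Each dose against the shared placebo arm (correlation 0.5): 0.0907 per covariate, so 1 − 0.9093^5 = 0.379 and 1 − 0.9093^10 = 0.614.

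**The case against.** An unadjusted primary test is a permissible choice, and by these figures it costs almost nothing at the design point. That stands, and it is why the point is minor. The documents show no weight gradient. Section 5.3 reports similar susceptibility to PCR-detected infection across age groups, which, if anything, argues against a strong one. A gain is more plausible for clinical malaria, which section 2.2.4 says falls with age, if weight tracks age (assumed).

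The plan also has its own use for weight. Section 4.3 states: "This study will test fixed doses of L9LS in children in a defined range of subject weights". The mg/kg dose therefore falls as weight rises, and the exploratory analysis studies that. If weight changes efficacy, stratifying can lose power, as Step 3 shows. This is a real cost of the fix. The exploratory analysis nevertheless does not adjust the arm-versus-placebo comparison.

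The covariate rule touches only an additional model. It responds to baseline imbalance rather than outcomes, and no effect of chance picks on the hazard ratio has been shown. That stands too. What remains is that the model's content is not fixed in advance.

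A reader might infer two stronger things. The first is that ignoring the strata inflates false positives; the null rows show at most the nominal rate. The second is that the unadjusted hazard ratio is biased toward 1. Step 4 shows that it correctly estimates the marginal hazard ratio, which lies slightly closer to 1 than the conditional one. The difference is one of estimand, and the PE used for sizing in 9.2.2 is itself unconditional.

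**Conclusion.** The point holds as a minor one. The analysis omits the factor used to stratify randomisation, and the supportive Cox model has an open covariate rule. The primary test remains valid and at worst conservative. The power cost is about 0 to 1 point at placebo 0.4 and PE 0.7, up to about 3 points at PE 0.6, and about 2 to 8 points only in the off-design row. All of these costs require weight to predict infection, with assumed steps of up to 2-fold. Adjustment does not narrow the confidence interval. The 23 to 61% chance of at least one spurious covariate rests on assumed numbers of independent candidates and concerns the additional model only.

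**What to change.** For Year 1, in section 9.5.4:

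1. Stratify the log-rank test by the three randomisation weight groups, summing within-group scores and variances. Include weight group in the interval-censored Cox model, and state that the resulting hazard ratio is conditional on weight group.
2. In the additional Cox model, replace the imbalance rule with a fixed list: weight group and time of enrollment.

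The parasitemia-stratified model and the mg/kg analysis can stay as they are.

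**Timing.** The synopsis plans Year 1 unblinding for about March/April 2023, and this version is dated 14 March 2024. If Year 1 is already unblinded, keep the planned analyses. Report the weight-stratified test and weight-adjusted model as labelled sensitivity analyses, and list the covariates that the imbalance rule picked.

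**Year 2.** Section 9.5.1.1 carries the same methods over, but section 4.1.1 re-randomises within original arm and states no weight strata. The weight-stratified test should not be carried over. Replace the imbalance rule with time of enrollment and, if weight is wanted, continuous Year 2 baseline weight. The Year 2 exclusions in 5.2.1 set no weight limit, so children may now exceed 30 kg and fall outside the original groups.

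**Cost.** SAP wording and additional analysis runs; weight group is known for every child randomised in Year 1. The power cost is about 0.1 to 0.3 points if weight is irrelevant. In the scenarios run it is up to about 1.6 points if weight modifies efficacy, including one where heavier children also have a 1.5-fold step in placebo risk.

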9.5.5 Safety Analyses

Safety analysis will be primarily MITT where individuals who receive assignment but do not receive any product are excluded. Because of blinding and the brief length of time between assignment and administration, such cases will be very few. In the rare case of subjects receiving a regimen different from assignment, an as-treated analysis will be additionally performed where subjects will be analyzed according to the product they actually receive.

Safety data will be presented by line listing and tables at the individual level to provide details on safety events such as severity, duration, and relationship to study product. The number and percentage of subjects with 1 or more AE(s) will be summarized by dose arm along with the exact 95% CIs of the AE rate. The number and percentage of subjects under each AE will be

Version Date: 14 March 2024

additionally reported. For subjects experiencing more than 1 AE, the subjects will be counted once under the event of highest severity.

In the efficacy study, comparisons between the dose arms and the control arm will be additionally performed in terms of the proportions of solicited AEs, related AEs, and SAEs.

In the rare case of subjects receiving a regimen different from assignment, a per-protocol analysis will be performed as a secondary analysis, which will include subjects according to the product they actually receive in the study.

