- 1. Dose escalation and efficacy: Incidence and severity of local and systemic AEs occurring within 7 days after the administration of L9LS.
- 2. Efficacy: Pf blood-stage infection as detected by microscopic examination of thick blood smears obtained between 1 week and 24 weeks after administration of L9LS or placebo.

Secondary Endpoints:

Data from both parts of this study will be used to assess the following endpoints:

- 1. Measurement of L9LS in sera of recipients.
- 2. Pf blood-stage infection as detected by RT-PCR for 28 weeks after administration of L9LS or placebo for dose escalation subjects or 24 weeks after administration of L9LS or placebo for efficacy subjects.

- 3. Incidence of clinical malaria (definition 1, see section 2.2.2.3) for 28 weeks after administration of L9LS or placebo for dose escalation subjects or 24 weeks after administration of L9LS or placebo for efficacy subjects.
- 4. Incidence of clinical malaria (definition 2, see section 2.2.2.3) for 28 weeks after administration of L9LS or placebo for dose escalation subjects or 24 weeks after administration of L9LS or placebo for efficacy subjects.
- 5. PK analysis of L9LS and the association of L9LS concentration with Pf infection risk.
- 6. PK analysis of L9LS and the association of L9LS concentration with clinical malaria risk.

Extension Phase Primary Endpoints:

- 1. Incidence and severity of local and systemic AEs occurring within 7 days after the administration of L9LS.
- 2. Measurement of L9LS in sera of recipients.
- 3. Measurement of ADA in sera of recipients.

Extension Phase Exploratory Endpoints:

- 1. Pf blood-stage infection as detected by microscopic examination of thick blood smears obtained between 1 week and 28 weeks after administration of L9LS or placebo.
- 2. Pf blood-stage infection as detected by RT-PCR from dried blood spots obtained between 1 week and 28 weeks after administration of L9LS or placebo.
- 3. Incidence of clinical malaria (definition 1, see section 2.2.2.3) between 1 week and 28 weeks after administration of L9LS or placebo.
- 4. PK analysis of L9LS and the association of L9LS concentration with Pf infection risk.
- 5. PK analysis of L9LS and the association of L9LS concentration with clinical malaria risk.

Study Population:

Healthy Malian adults (aged ≥18 to 55 years) and children (aged 6 to 10 years) residing in Kalifabougou and Torodo who are not receiving seasonal malaria chemoprevention (SMC).

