8.4 Safety Definitions, Management, and Sponsor Reporting

8.4.1 Definitions

Adverse Event: An AE is any untoward or unfavorable medical occurrence in a human subject, including any abnormal sign (e.g., abnormal physical exam or laboratory finding), symptom, or disease, temporally associated with the subject's participation in the research, whether or not considered related to the research.

Adverse Reaction: An AR means any AE caused (see "Causality" below) by a study agent. ARs are a subset of all suspected adverse reactions (SARs; defined below) where there is reason to conclude that the study agent caused the event.

Version Date: 14 March 2024

Suspected Adverse Reaction: SAR means any AE for which there is a reasonable possibility that the study agent caused the AE.

Per US FDA guidance:

For the purposes of IND safety reporting, "reasonable possibility" means there is evidence to suggest a causal (see "Causality" below) relationship between the study agent and the AE. A SAR implies a lesser degree of certainty about causality than an AR, which means any AE caused by a study agent.

SARs are the subset of all AEs for which there is a reasonable possibility that the study agent caused (see "Causality" below) the event. Inherent in this definition, and in the requirement to report SARs, is the need for the sponsor to evaluate the available evidence and make a judgment about the likelihood that the study agent actually caused the AE.

The sponsor is responsible for making the causality judgment.

Serious Adverse Event: An SAE:

- is an AE that results in death.
- is an AE that is life-threatening event (places the subject at immediate risk of death from the event as it occurred).
- is an AE that requires inpatient hospitalization or prolongs an existing hospitalization. NOTE:
 - Hospitalization is considered required if outpatient treatment would generally be considered inappropriate.
 - o Same-day surgical procedures that are required to address an AE are considered hospitalizations, even if they do not involve an overnight admission.
 - O Hospitalization due to a condition that has not worsened and that pre-dates study participation (e.g., elective correction of an unchanged baseline skin lesion), or due to social circumstance (e.g., prolonged stay to arrange aftercare), or that is planned/required "per protocol" AND that proceeds without prolongation or complication, is NOT considered an SAE by this criterion.

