8.4.2 Documenting, Assessing, Recording, and Reporting Events

ALL AEs, including those that may appear to have a non-study cause (see "Causality" below), will be documented (e.g., on the clinical chart/progress notes/clinical laboratory record), recorded (e.g., in the study-specified CRF/research database), and reported (e.g., cumulatively from the research database, or according to protocol-specified expedited reporting mechanism) to the sponsor from the time informed consent is obtained through the timeframe specified below. At each contact with the subject, information regarding AEs will be elicited by open-ended questioning and examinations.

AEs and SAEs will generally be recorded, assessed, and reported according to the timeframes outlined in Table 2.

Version Date: 14 March 2024

Table 2. Standard event recording, assessment, and reporting timeframes.

Event type	Record, assess, and report through
Related SAEs	End of subject participation in study, or if study personnel become aware thereafter
Unrelated SAEs	End of subject participation in study
Related non-serious AEs of grade 1 to 3	End of subject participation in study
All other related non- serious AEs	End of subject participation in study
Unrelated non-serious AEs	End of subject participation in study

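### Section 9.5.5 sets no window and no malaria rule, so SAE comparisons, AE summaries after Day 7 and Year 2 safety contrasts would absorb prevented malaria and could mask other harms.

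*Combined protocol and SAP*

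**What the plan says.** The Synopsis and Sections 3 and 9.1 define the primary safety endpoint as "Incidence and severity of local and systemic AEs occurring within 7 days after the administration of L9LS". Section 9.5.2 then hands over: "Analysis for the primary endpoint for safety and tolerability is described in section 9.5.5".

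Section 9.5.5 plans three things that matter here:

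- An overall summary with exact 95% CIs: "The number and percentage of subjects with 1 or more AE(s) will be summarized by dose arm".
- A per-event table ("The number and percentage of subjects under each AE will be" reported as well), with the rule that, for a child with several AEs, "the subjects will be counted once under the event of highest severity".
- Formal contrasts, planned for the Year 1 efficacy part only: "comparisons between the dose arms and the control arm will be additionally performed in terms of the proportions of solicited AEs, related AEs, and SAEs".

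None of these carries a time window, and the section is silent on malaria.

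On what is collected, Section 8.4.1 states that "An AE is any untoward or unfavorable medical occurrence in a human subject", names disease among the examples, and makes no exception for malaria. Section 8.4.2 requires recording of "ALL AEs, including those that may appear to have a non-study cause", and Table 2 runs to the end of participation for every event type. Section 8.4.2.2 records a diagnosed illness under its diagnosis.

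For Year 2, Section 9.5.1.1 carries the same methods forward. Section 4.1.1 plans safety evaluations of 1a vs 1b, 2a vs 2b, 3a vs 3b and 1a vs 3a, and of all L9LS against all placebo (1a+2a+3a vs 1b+2b+3b).

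**The concern.** A symptomatic malaria episode is an AE, and a hospitalised one is an SAE. The same episode can also count towards the clinical-malaria efficacy endpoints. The efficacy window opens at week 1, just as the 7-day safety window closes, so the window chosen for a safety table decides whether malaria enters it.

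If L9LS works, it lowers any pooled AE or SAE proportion by preventing malaria. An excess of other events can then look like no difference, or like fewer events than on placebo. Later safety is of real interest in this plan. Section 2.2.3 gives an estimated half-life of 56 days and raises reactions driven by anti-drug antibodies, and Section 2.3.1 commits to watching for salivary-gland effects and describes delayed allergic reactions.

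Year 2 adds a complication. Section 2.2.4 raises rebound malaria in children given L9LS and then placebo. Those children (1b and 2b) are in the pooled placebo group, so rebound would raise the comparator's event rate and make L9LS look safer.

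**Working it through.** **1. The plan's own safety figures.** Table 6 gives exact CIs for 42 per arm. Clopper-Pearson limits match all 15 rows. For 0/42 the upper limit is 1 - 0.025^(1/42) = 0.084, as printed. There is no arithmetic error; the issue is which events are counted.

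**2. Which planned outputs contain malaria.**

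| Output | Malaria included? |
|---|---|
| AEs within 7 days (primary endpoint) | Very little: artemether-lumefantrine is given first and the window is short |
| Related AEs | Largely not: Section 8.4.2.1.2 classes an event with a better alternative cause as unlikely or not related |
| SAE comparison | Yes, when malaria meets an SAE criterion |
| Any-AE proportion beyond Day 7 | Yes |
| Count under the most severe event | Yes: a child with a mild reaction and worse malaria is counted under malaria |
| Year 2 contrasts of L9LS with placebo | Yes, unless restricted to 7 days or to related events |

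**3. Size for AEs after Day 7 (illustration).** Inputs:

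- Protective efficacy 0.7, a planning value in Section 9.2.2, assumed to apply to malaria AEs.
- Placebo malaria-AE rate m of 0.20, 0.30 or 0.40 (assumed). The top value equals the planning infection rate in Section 9.2.2.
- Other AEs 0.30 on placebo and 0.50 on L9LS (assumed).
- Malaria and other AEs independent (assumed).

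Formula: any AE = 1 - (1 - malaria)(1 - other), with malaria on L9LS = 0.3m.

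| m | Placebo any AE | L9LS any AE | Apparent difference |
|---|---|---|---|
| 0 | 0.30 | 0.50 | +20 points |
| 0.20 | 1 - 0.80×0.70 = 0.44 | 1 - 0.94×0.50 = 0.53 | +9 |
| 0.30 | 1 - 0.70×0.70 = 0.51 | 1 - 0.91×0.50 = 0.545 | +3.5 |
| 0.40 | 1 - 0.60×0.70 = 0.58 | 1 - 0.88×0.50 = 0.56 | -2 |

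Sensitivity: with efficacy 0.6 the differences are +10, +5 and 0; with 0.8 they are +8, +2 and -4. With other AEs of 20% v 40% and efficacy 0.7 they are +7.6, +1.4 and -4.8.

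For scale in Year 2, Section 9.3 quotes 90% power with 42 per arm for 0.01 v 0.24, 0.05 v 0.33 and 0.10 v 0.42, which are gaps of 23, 28 and 32 points. The illustration loses 20 - 9 = 11 to 20 - (-2) = 22 points.

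**4. Size for SAEs (illustration).** Let s be the placebo rate of malaria SAEs, with no other placebo SAEs and efficacy 0.7. The pooled SAE rates are equal when other SAEs on L9LS are 1 - (1 - s)/(1 - 0.3s):

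- s = 0.01: 0.7%
- s = 0.02: 1 - 0.98/0.994 = 1.4%
- s = 0.04: 2.8%

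In 75 children these are about 0.5, 1 and 2 children.

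**5. Whether the per-event rows repair this.** A malaria row would be visible, but the non-malaria proportion cannot be recovered from it. If children can appear in several rows, the rows cannot be subtracted from the total. If each child is counted once under the worst event, removing the malaria row also removes that child's milder non-malaria AEs.

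**The case against.** A reader might infer that Section 9.5.5 counts every AE over full follow-up, so that the primary safety result itself restates efficacy. The documents do not support that. The section never says full follow-up. The 7-day limit belongs to the endpoint that Section 9.5.2 assigns to it, and Table 2 sets a recording period, not an analysis window. Read naturally, the primary safety analysis covers 7 days and contains little malaria.

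Several further points stand:

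- In Year 1, any-AE is summarised with CIs but is not among the planned between-arm comparisons.
- Related AEs should mostly exclude malaria. Solicited AEs are exposed only if symptoms such as fever and headache are counted beyond the first week.
- Malaria would have its own row, and the line listings show severity and relationship.
- Each SAE is reported individually to the safety office, the independent monitor and the DSMB, so one or two unusual SAEs are unlikely to go unseen.
- The rates are assumed. The historical 85% is PCR-detected infection, not illness, and cannot serve as a malaria-AE rate.

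All-cause SAEs are also a legitimate measure of net harm, and in Year 2 malaria after earlier L9LS may itself be a harm. That argues against removing malaria from the main safety comparison. It does not argue against showing both versions.

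**Conclusion.** The concern holds in limited form. The 7-day primary endpoint is largely unaffected, and its missing window in Section 9.5.5 is only a lack of detail. The substantive gap is that the SAE comparison, AE summaries beyond Day 7, the most-severe-event count and the Year 2 contrasts of L9LS with placebo pool malaria with everything else, and no non-malaria total is planned. Contrast 1a vs 3a is less exposed, because both groups receive L9LS in Year 2.

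The direction follows from the definitions whenever L9LS prevents symptomatic malaria. The size is illustrative only: a 20-point excess shown as about +9 to -2 points rests on assumed AE rates, placebo malaria AEs of 20% to 40%, efficacy of 0.7 carrying over to malaria AEs, and independence. For SAEs the masked excess is small in absolute terms, at 0.7 to 2.8 percentage points under the assumed rates.

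**What to change.** In Section 9.5.5:

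1. Label the Day 0-7 table as the primary safety analysis, and tabulate later AEs separately.
2. For AEs after Day 7 and for SAEs, give the proportions with exact CIs, the severity counts and the planned between-arm comparisons twice, side by side: all-cause and excluding Pf malaria. Put malaria in its own row and designate neither version as main.
3. Define malaria events by a rule fixed blind to arm, for example a smear-positive illness.
4. Apply the same layout to Year 2, with malaria shown by sub-arm so that any rebound in 1b and 2b stays visible.

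The data are already collected. The cost is analysis-plan wording, one extra set of tables and the blinded classification rule, which needs some judgement about complications of malaria.
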